### 7.6.2 Serology

A test for Hepatitis B surface antigen, Hepatitis C virus and HIV (anti-HIV1/2 and p24 antigen) will be done at Screening. In case of positive results, the subject will be referred to appropriate medical care.

### 7.6.3 Urine Drug Screen

A urine drug screen will be performed at the site at the Screening Visit and at the day of Admission. The urine will be screened for amphetamines, barbiturates, benzodiazepines, cannabinoids, cocaine, and opiates.

Confidentiality Statement: Data and information contained in this document are considered to constitute trade secrets and confidential commercial information, and the legal protections provided to such trade secrets and confidential information are hereby claimed under the applicable provisions of applicable law. No part of this document may be publicly disclosed without the written consent of Philip Morris Products SA.

#### 7.6.4 Urine Cotinine Screening

A urine dip-stick cotinine test will be performed at Screening and at Admission to the clinic in order to confirm the subject's smoking status. The test must detect cotinine with a cotinine of  $\geq 200$  ng/mL, (i.e., One-Step Cotinine Test 008A086, Ultimed, Belgium).

#### 7.6.5 Alcohol Breath Test

Subjects will undertake a breath alcohol test at the Screening Visit and at Admission to the clinic using a newly calibrated alcometer device (e.g., Alcotest 7410 Plus, Dräger).

#### 7.6.6 Urine Pregnancy Testing

All female subjects will have pregnancy testing at the Screening Visit, at Admission to the clinic, and at the Day of Discharge (Day 4). Female subjects with a positive pregnancy test at the Screening Visit or on Day -1 cannot be enrolled and are considered a screening failure. Pregnancy in such subjects will not be followed up as no exposure to the THS 2.2 will have occurred. Product test at Admission must be done only in female subjects with a negative pregnancy test. In any case of a positive pregnancy test, the Investigator will inform the subject about the risks associated with smoking during pregnancy. In the event of unclear urine pregnancy test in peri-menopausal women, absence of pregnancy should be confirmed by a serum follicle stimulating hormone level  $>20$  IU/l.

All pregnancies detected during the study must be reported and handled as described in [Section 8.5](#).

### 7.7 Sample Handling, Storage, and Shipment

Participating laboratories for blood samples testing will be decided prior to investigator meeting and site initiation. Safety laboratory samples will be tested at a local laboratory (see [Appendix 2](#)). The urine dipstick for the safety laboratory, urine drug screen, urine pregnancy tests and urine cotinine tests will be done by the site personnel at the site. The tests will be provided by the sites.

Detailed procedures for handling of samples are described in the separate sample handling manual (SHM). Safety laboratory samples will be destroyed as by the laboratories standard procedures. All other samples will be destroyed once the CSR has been finalized. The facility/-ies at which the samples are stored will be informed in writing by the Sponsor when destruction of the samples shall be performed.

#### Blood samples

Confidentiality Statement: Data and information contained in this document are considered to constitute trade secrets and confidential commercial information, and the legal protections provided to such trade secrets and confidential information are hereby claimed under the applicable provisions of applicable law. No part of this document may be publicly disclosed without the written consent of Philip Morris Products SA.

Blood samples will be drawn by qualified and trained site personnel. Subjects should be in a seated position during blood collection. In total, around 260 mL will be drawn for this study including planned assessments, safety, and repeated analysis for safety. The required aliquots and volumes for assessments of blood/plasma parameters and tests are summarized in the SHM.

### Urine samples

Spot urine samples will be taken for urine drug screen, cotinine screen, pregnancy tests and safety urinalysis.

## 7.8 Questionnaires

The subject questionnaires and the VAS will be entered by the subject directly in the electronic patient reported outcomes device or in paper copy. The questionnaires and the VAS will be reviewed for completeness by the study site staff and subjects will be requested to complete any missing information.

Symptoms or worsening of symptoms as documented on any of the questionnaires or the VAS do not need to be documented as AEs because the questionnaire and the VAS will be analysed as part of the report. However, it is at the discretion of the Investigator to document such symptoms also as AEs. The main source for AE collection will be the face-to-face interview between the subject and site staff using, open, non-directive questions (see section [Section 8](#)).

### 7.8.1 Fagerström Test for Nicotine Dependence (revised version)

Potential nicotine dependence will be assessed at Screening using the FTND in its revised version ([Heatherton et al, 1991](#)), as updated in 2012 ([Fagerström et al, 2012](#)).

The questionnaire consists of six questions which have to be answered by the subject himself/herself. The scores obtained on the test permit the classification of nicotine dependence into three levels: Mild (0 to 3 points); Moderate (4 to 6 points); Severe (7 to 10 points) ([Fagerström et al, 2012](#)).

### 7.8.2 Assessment of Cough

Subjects will be asked if they have experienced a regular need to cough e.g. coughing several times in the last 24 hours prior to assessment. If the answer is 'yes', they will be asked to complete a VAS, three Likert scales and an open question also assessing the previous 24 hours.

Confidentiality Statement: Data and information contained in this document are considered to constitute trade secrets and confidential commercial information, and the legal protections provided to such trade secrets and confidential information are hereby claimed under the applicable provisions of applicable law. No part of this document may be publicly disclosed without the written consent of Philip Morris Products SA.

The VAS will assess how bothersome cough is to the subject ranging from 'not bothering me at all' to 'extremely bothersome'.

Furthermore, subjects will be asked to assess the intensity and frequency of cough and the amount of sputum production on Likert scales:

- The intensity of cough will be assessed on a 5-point Likert scale ranging from 1 to 5: 1 = very mild; 2 = mild; 3 = moderate; 4 = severe; 5 = very severe.
- The frequency of cough will be assessed on a 5-point Likert scale ranging from 1 to 5: 1 = rarely; 2 = sometimes; 3 = fairly often; 4 = often; 5 = almost always.
- The amount of sputum production will be assessed on a 4-point Likert scale ranging from 0 to 3: 0 = no sputum; 1 = a moderate amount of sputum; 2 = a larger amount of sputum; 3 = a very large amount of sputum.

Finally, subjects will be asked with an open question if there are any other important observations that they would like to share with the staff about their coughing.

Assessments will be done on a daily basis from Day 0 to Day 4. On Day 2 and Day 4, questionnaire must be asked 24 hours after T0 of Day 1 and after 24 hours minus 5 minutes after T0 of Day 3.

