#### 12.1.2 Definitions for Statistical Data Analysis

Unless otherwise stated, for the purposes of statistical analyses, baseline is defined as the last available time point prior to  $T_0$  on Day 1, from 6:00 AM to 9:00 AM.

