#### 12.1.4 Handling of Missing Values and of Values outside the Detection Limits

In general, missing data will not be imputed in this study, due to the nature of the measurements and the short periods of exposure and use. However, for questionnaire data total scores and domain or subscale scores may use a certain degree of imputation by averaging across individual item scores. Further details will be provided in the SAP.

Values below the lower limit of quantification (LLOQ) will be imputed using  $0.5 \times$  lower limit of quantification. For values above the upper limit of quantification (ULOQ), i.e., preceded by a “>”, for example “>xx”, the numerical xx will be used for calculation and reporting in summary tables. The number of values below LLOQ or above ULOQ will be presented in each summary table.

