#### 12.6.5 Safety Endpoints

In general, all safety data will be listed and tabulated on the safety population by sequence, using the approach described in [Section 12.1.3](#). Safety variables collected during exposure periods will also be reported by product exposure.

AEdatas will serve as the primary assessment of safety. Other safety variables monitored in this study include: respiratory symptoms (cough assessment VAS and Likert scales); vital signs (systolic and diastolic blood pressure, pulse rate, respiratory rate); spirometry; ECG data; clinical chemistry, haematology, and urine analysis safety panel; physical examination; and concomitant medication.

The number and percentage of subjects with AEs and SAEs will be tabulated by system organ class and preferred term. Summaries will also be presented for AEs leading to withdrawal, AEs leading to Death, AEs by relatedness to product exposure, AEs by severity, and laboratory AEs. Tabulations will be performed for both the number of subjects experiencing an event and the number of events. The number and percentage of device events and of subjects with device events will be tabulated by sequence.

Confidentiality Statement: Data and information contained in this document are considered to constitute trade secrets and confidential commercial information, and the legal protections provided to such trade secrets and confidential information are hereby claimed under the applicable provisions of applicable law. No part of this document may be publicly disclosed without the written consent of Philip Morris Products SA.

The number and percentage of subjects with clinical findings will be tabulated by sequence for laboratory parameters. Shift tables showing change from baseline of clinical findings will be provided for ECGs, physical examinations, and laboratory parameters (both shifts in normal ranges and toxicity grades). Descriptive statistics will be summarized by visit and change from baseline for laboratory parameters, ECG, respiratory symptoms, and vital signs.

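### The cough change-from-baseline summary covers only subjects who cough at both times; tabulate the yes/no cough answer, with a shift table, as the main respiratory-symptom summary

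*Protocol*

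**What the plan says.** Protocol section 7.8.2 sets a filter question on regular cough over the previous 24 hours. The scales follow only a positive answer: "If the answer is 'yes', they will be asked to complete a VAS, three Likert scales and an open question". Neither the intensity scale, "ranging from 1 to 5: 1 = very mild", nor the frequency scale, "ranging from 1 to 5: 1 = rarely", has a value for no cough. The sputum scale starts at 0. On timing: "Assessments will be done on a daily basis from Day 0 to Day 4".

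Section 12.1.4 states: "In general, missing data will not be imputed in this study". The exception it names is that "for questionnaire data total scores and domain or subscale scores may use a certain degree of imputation by averaging across individual item scores", with details left to the SAP.

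Section 12.1.2 sets the reference point: "baseline is defined as the last available time point prior to" T0 on Day 1.

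Section 12.6.5 identifies respiratory symptoms with the cough VAS and Likert scales and plans: "Descriptive statistics will be summarized by visit and change from baseline for laboratory parameters, ECG, respiratory symptoms, and vital signs". It lists shift tables for ECG, physical examination and laboratory parameters, but not for cough.

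Section 7.8 adds that symptoms reported on the questionnaires or the VAS need not be recorded as adverse events, because those instruments will be analysed in the report. Recording them is left to the investigator's discretion.

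**The concern.** Cough is the respiratory-symptom safety variable named in section 3.4. The case of most interest is a subject who does not cough before product use and coughs afterwards. That is a realistic case here: the nasal spray label in Appendix 4 lists coughing as common, and names cough among the nasal irritation symptoms that 94% of patients reported in the first two days.

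That subject has no baseline score, so no change can be computed. A subject whose cough resolves has no later score and is lost in the same way. The change column therefore describes persistent coughers, a subset that can differ between products. A reader could take a small change in that column as evidence that a product does not affect cough. The relaxed adverse event recording in section 7.8 increases the weight placed on this summary.

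**Working it through.** No figure in the protocol is there to be reproduced; the check is to follow the rules through.

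**Step 1. Which subjects have a change score.** Inputs: scales completed only after 'yes' (7.8.2), no imputation in general (12.1.4), change = later score minus baseline score (12.6.5).

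| Baseline answer | Later answer | Baseline score | Later score | Change |
|---|---|---|---|---|
| yes | yes | present | present | computable |
| no | yes (new onset) | absent | present | none |
| yes | no (resolved) | present | absent | none |
| no | no | absent | absent | none |

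The exception in 12.1.4 averages over items that were answered. It cannot supply a score when the whole set was skipped.

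The baseline definition leaves one complication. A subject answering 'yes' on Day 0 and 'no' on Day 1 might be given the Day 0 score as the last available one. That would be a stale baseline for a recurrent cough. A subject answering 'no' on both days has no baseline score on any reading.

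**Step 2. How many coughers are omitted.** The documents give no cough rates, so all rates here are assumptions. Let p be baseline prevalence, r the share of baseline coughs that resolve, and o the onset rate among those without cough at baseline.

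- Persistent: p(1 − r)
- Resolved: p·r
- New onset: (1 − p)·o
- Share of ever-coughers omitted: [p·r + (1 − p)·o] / [p + (1 − p)·o]

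With p = 10%, r = 50%, o = 10% and all 62 randomised subjects:

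- persistent 62 × 0.10 × 0.50 = 3.1
- resolved 62 × 0.10 × 0.50 = 3.1
- new onset 62 × 0.90 × 0.10 = 5.6
- omitted (3.1 + 5.6) / (3.1 + 3.1 + 5.6) = 74%

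Over p from 5% to 30%, o from 2% to 20% and r of 20% or 50%, the omitted share runs from 24% (p = 30%, o = 2%, r = 20%) to 90% (p = 5%, o = 20%, r = 50%).

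**Step 3. What the tables would show.** Assume 62 subjects and 6 baseline coughers, of whom 3 persist unchanged and 3 resolve, plus 9 new coughs, all at intensity 3.

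- Coughers rise from 6 to 3 + 9 = 12.
- Planned change summary: n = 3, mean 0.00.
- By-visit summary: mean 3.0 at both times, but n rises from 6 to 12.
- For comparison only, with 'no' scored 0: (9 × 3 − 3 × 3) / 62 = +0.29.

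The change column misses the doubling; the by-visit n shows it. The zero mean follows from assuming that persistent coughers do not change. The omission itself does not depend on that assumption.

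**The case against.** A reader might infer that the planned tables cannot reveal new cough at all. The documents do not support that. Section 12.1.3 requires n and the number and percentage missing, by exposure at each time point where applicable, so a rise in cough would appear as a larger n. New-onset scores enter the by-visit statistics. Section 12.6.5 makes adverse event data the primary assessment of safety, and section 8.2 provides active collection by interview, which questionnaire review may also trigger.

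A reader might also infer that imputation is forbidden. Section 12.1.4 says 'in general' and defers details to the SAP, which is not at hand and could define a score for 'no'. This stands as a limit. The protocol itself, however, commits to a change from baseline on scales that do not exist without cough, and offers no rule that would fill them.

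A third inference is that 'no' must be scored 0. That does not follow. The question concerns a regular need to cough, so 'no' does not establish zero cough or zero sputum. On the VAS, a 0 would also merge non-coughers with coughers who are not bothered.

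Finally, the amended protocol text available stops within section 7.7, so sections 7.8.2 and 12 can be read only in the original version. The amendment's itemised changes do not touch them, although the amended text also differs in places that are not itemised, such as Table 1.

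**Conclusion.** The point holds, within limits. As written, the change-from-baseline summary for cough is restricted to subjects with cough at both times and omits new onset and resolution. By-visit scores are severity among coughers, with an n that still carries the count. This follows from sections 7.8.2, 12.1.4 and 12.6.5 and needs no assumed rate. The size does: 24% to 90% of ever-coughers omitted is an illustration over assumed rates.

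The consequence is confined to one descriptive safety summary. No hypothesis test and no primary PK result is affected, and adverse event collection remains. It is worth correcting because the yes/no answer is already collected, while the protocol names neither an incidence table nor a shift table for it.

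**What to change.** In section 12.6.5:

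- Make the yes/no cough answer the main respiratory-symptom summary, tabulated for all subjects asked, by product exposure and visit.
- Add a shift table of the answer before use (Day 1, Day 3) against the answer at the matching 24-hour assessment (Day 2, Day 4), to show new onset and resolution.
- Present the VAS and Likert scores as severity among subjects with cough, and label any change score as limited to subjects with cough at both times.
- A summary scoring 'no' as 0 may be added as supplementary, but should not be required.

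Cost: one or two extra descriptive tables from data already collected, with no new assessments.

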### 7.8.3 Modified Cigarette Evaluation Questionnaire (modified version)

Product evaluation will be assessed using the MCEQ ([Cappelleri et al, 2007](#)). The MCEQ assesses the degree to which subjects experience the reinforcing effects of smoking, by measuring:

- Smoking satisfaction (satisfying, tastes good, enjoy smoking).
- Psychological rewards (calms down, more awake, less irritable, helps concentrate, reduces hunger).
- Aversion (dizziness, nauseous).
- Enjoyment of respiratory tract sensations (single-item assessment).
- Craving reduction (single-item assessment).

Confidentiality Statement: Data and information contained in this document are considered to constitute trade secrets and confidential commercial information, and the legal protections provided to such trade secrets and confidential information are hereby claimed under the applicable provisions of applicable law. No part of this document may be publicly disclosed without the written consent of Philip Morris Products SA.

This questionnaire will only be completed by the subjects, who use the THS 2.2 or smoke CC during the study in sequence 1 and 2. The MCEQ will be completed by subjects on Day 1 and Day 3.

#### 7.8.4 Questionnaire of Smoking Urges (QSU-brief)

To assess the urge-to-smoke, all subjects will be asked to complete a 10-item brief version of the QSU-brief (Cox et al, 2001). The QSU-brief is a self-reported questionnaire with 10 items to be rated on a 7-point scale, ranging from 1 (strongly disagree) to 7 (strongly agree). Higher scores in this questionnaire indicate a higher urge to smoke.

The findings in this brief version were consistent with the expressions of craving found in the 32-item version of the QSU-brief (Tiffany et al, 1991). The findings supported a multi-dimensional conceptualization of craving to smoke and demonstrated the utility of a brief multi-dimensional measure of craving (Cox et al, 2001).

The QSU-brief will be completed by the subject himself/herself at single use study days (D1, D3). The first assessment will be done prior to T0. All other assessments will be done after T0, at 15 minutes, 30 minutes, 45 minutes, 1 hour, 2 hours (with an allowed time window of +5 min each) and 4 hours, 6 hours, 9 hours, 12 hours (with an allowed time window of +10 min each).

#### 7.8.5 Socio-Economic Questionnaire

At Screening, subjects will fill a questionnaire, which will allow the Sponsor to assign the subject household's SES. Subjects will be asked a series of questions related to their education, occupation, and household. Then they will be asked a series of questions to assess the occupation, employment status and qualifications of the Chief Income Earner of their household that is the person with the largest income. The questionnaire will be administered by a trained interviewer.

The social grading classification that will be used to determine the subject household's SES is based upon the occupation and employment status of the Chief Income Earner (Meier & Moy, 2004). Based on the answers of the subjects, data will be recoded in order to assign the head of the household to one of the following socio-economic classes:

Grade	Social class
A	upper middle class
B	middle class

Confidentiality Statement: Data and information contained in this document are considered to constitute trade secrets and confidential commercial information, and the legal protections provided to such trade secrets and confidential information are hereby claimed under the applicable provisions of applicable law. No part of this document may be publicly disclosed without the written consent of Philip Morris Products SA.

---

- C1 lower middle class
- C2 skilled working class
- D working class
- E Those at the lowest levels of subsistence

Confidentiality Statement: Data and information contained in this document are considered to constitute trade secrets and confidential commercial information, and the legal protections provided to such trade secrets and confidential information are hereby claimed under the applicable provisions of applicable law. No part of this document may be publicly disclosed without the written consent of Philip Morris Products SA.

## 8 ADVERSE EVENTS

### 8.1 Definitions

#### 8.1.1 Adverse Events

The FDA MRTP guidelines specify the following definition for adverse events for tobacco products([FDA, 2012a](#)):

An AE is any health-related event associated with the use of a tobacco product in humans, which is adverse or unfavourable, whether or not it is considered related to the tobacco product, as defined by the MRTP guidelines.

An AE is defined as any untoward medical occurrence in a subject, or clinical investigation subject administered an IP, which does not necessarily have a causal relationship with the IP or reference point product. An AE can therefore be any unfavourable and unintended sign (including a clinically relevant abnormal laboratory finding), symptom, or disease temporally associated with the use of an IP or reference point product, whether or not to the IP or reference point product

#### 8.1.2 Serious Adverse Events

An SAE is defined as, but not limited to, any untoward medical occurrence that:

- Results in death.
- Is life-threatening.
- Requires inpatient hospitalization or prolongation of existing hospitalization.
- Results in persistent or significant disability/incapacity, or
- Is a congenital anomaly/birth defect.

Important medical events that may not result in death, be life-threatening, or require hospitalization may be considered an SAE when, based on appropriate medical judgment, they may jeopardize the subject or the subject may require medical or surgical intervention to prevent one of the outcomes listed in the above definitions.

Any pre-planned hospitalizations that are known at the time of signing the ICF will not be recorded as SAEs; however, they will be recorded as AEs only. Any AE that occurs during this pre-planned hospitalization will be considered according to the above definitions.

